## **2.2 CO-PRIMARY ENDPOINTS**

### Functional Endpoint

Assessment of primary patency rate at 9-months, defined as continuous patency without the occurrence of a total occlusion of the original lesion, without a re-intervention to treat a partial or total occlusion of the stented segment, or bypass of the stented segment due to clinically-driven restenosis or occlusion.

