## 2.0 TRIAL OBJECTIVES

### 2.1 RATIONALE

The primary goal of revascularization therapy is the re-establishment and maintenance of adequate blood flow within the renal artery to perfuse the kidney. ARTISAN will investigate the re-establishment of adequate blood flow and normalized pressure in the renal artery and its effect on blood pressure in patients with resistant hypertension. In this single-arm trial, primary endpoints have been determined to show the safety, effectiveness, and clinical outcomes of the iCAST™ RX Stent System. Safety and effectiveness will be evaluated based on the primary patency rate at 9-months on a per lesion basis evaluated against a performance goal of published studies with bare-metal stents. The primary clinical endpoint will assess the improvement in SBP at 9-months as compared to baseline SBP.

The primary functional endpoint of primary patency has been established since the clinical care of the physician is considered a more objective measurement of stent performance than the restenosis measurement of DUS alone. In standard practice, a DUS is used to determine patency of a stent. If a DUS is negative and the patient is asymptomatic, no intervention is typically conducted by a physician. If a patient is symptomatic or a DUS is positive, a confirmatory angiogram is typically performed to assess the patency of the vessel.

To properly match the functional outcomes with historical data, the endpoint will be calculated on a per lesion basis. This reflects the current standard of care of treating patients with single

vessel renal artery lesions and those patients with bilateral renal artery stenosis. Analysis of past studies has demonstrated that the number of lesions treated per patient has increased with time. A recent renal trial reported 1.2 lesions per patient were treated. To calculate on a per patient level for this endpoint would bias the results and overestimate the failure rate compared to a per lesion analysis, as more lesions would be at risk for restenosis but would not be accounted for in a per patient analysis.

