### 5.2.1 DERIVATION OF THE PERFORMANCE GOAL FOR PATENCY

The Performance Goal was derived from a thorough literature review of trials with renal bare metal stent placement. Trials were identified by means of a PUBMED search of the English-language medical literature from 1991 to 2010. When available, the following data were extracted: author and year of publication, number of subjects, number of

arteries, restenosis definition, evaluation method, duration of follow-up, and restenosis rate. Of the 30 articles reviewed, 9 articles were excluded from the Performance Goal based on the following: results from studies with data collection from the 1980's which is not representative of today's standard of care, definitions used for restenosis were outside of our trial design, follow-up occurred at times outside of our assessments, and results from studies not yet published.

The following references were deemed relevant for the patency Performance Goal:

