**Table 3: Derivation of Patency Performance Goal**

Author	Year	Number of Subjects	Number of Arteries	Evaluation Method	Follow-up Time	Restenosis Rate
Rocha -Singh et al 	2005	208	252	DUS	9 mo	17.4%
Laird et al 	2010	188	188	DUS	9-12 mo	16.8%
Fleming et al 	2010	30	66	Angio	6 mo	35%
Corriere et al 	2009	91	101	DUS	12 mo	26.7%
Rocha-Singh et al 	2008	100	117	DUS	9 mo	21.3%
Nolan et al 	2005	78	97	DUS	12 mo	25%
Nolan et al 	2005	82	96	DUS	12 mo	25%
Sapoval et al 	2005	52	52	Angio	6 mo	14%
Shammas et al 	2004	58	58	DUS, Angio, CTa	2-20 mo	26%
Lederman et al 	2001	300	358	Angio	16 mo	21%
Symonides et al 	1999	27	27	DUS, Angio to confirm	6 mo	30%
Van de Ven et al 	1999	42	51	Angio	6 mo	14%
Rundback et al 	1998	45	32	Angio	12 mo	25%
Tullis, et al 	1997	41	52	Angio/DUS	12 mo	44%
Harden et al 	1997	32	33	Angio	6 mo	12%
White et al 	1997	100	133	Angio	6-12 mo	19%
Iannone et al 	1996	63	86	DUS	12 mo	14%
Dorros et al 	1995	76	92	Angio	6 mo	25%
Hennequin et al 	1994	21	25	Angio	12 mo	19%

The weighted mean restenosis rate from these trials is 21.4%. Assuming a restenosis rate for PTRA of 40% as noted in Carr based on the analysis of 6 trials with PTRA and also used by Rocha-Singh, a restenosis rate of 30% leading to a Performance Goal for primary patency set at 70%. This goal will preserve at least 50% of the difference between the currently available bare metal stent rate and the PTRA rate, as well as adjust for a lesion set with a higher percentage stenosis (80%-100%) than previous reported studies (50%-100%).

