5. STUDY DESIGN

5.1 General Design

This is a prospective, single-arm, multicenter clinical trial that will take place at up to 25 US/OUS sites. Primary endpoints have been determined to show the safety, effectiveness, and clinical outcomes of the iCAST™ RX Stent System.

After meeting screening and clinical eligibility criteria, subjects will undergo a baseline assessment for angiographic eligibility. After angiographic documentation of a $\geq 80\%$ diameter renal artery stenosis or Fraction Flow Reserve (FFR) < 0.8 is confirmed, the subject may be enrolled in the trial by placement of the investigational device.

Primary endpoint data is obtained at the 9-month visit and will include a follow-up Duplex Ultrasound (DUS) of the target renal artery(s). If the DUS is indicative of $\geq 60\%$ stenosis as determined by the core laboratory, or the DUS measures are non-diagnostic, a contrast enhanced angiogram will be used to assess the degree of restenosis of the covered stent(s).

Follow-up will be required for all treated subjects as detailed in Section 6.

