7.6 Endpoints, Safety Outcomes and Other Parameters

7.6.1.Primary Endpoints

Primary Patency Rate

In order to mitigate the challenges with DUS interpretation, clinical validation through independent noninvasive core laboratory and/or angiography will be performed in order to correctly validate and definitively assess percent diameter stenosis. DUS is highly reliable in identifying widely patent stents – however, correlation studies of DUS with angiography have confirmed that DUS is not as accurate when results suggest a stenosis. To lessen the risk of inaccurate readings, if a stenosis is detected in DUS (RAS > 60%) or if the DUS is non-diagnostic due to an imaging quality problem then a contrast angiogram will be used to assess the degree of restenosis of the covered stent(s) at the 9-month visit (± 30 days).

The primary efficacy variable is the primary patency rate, defined as continuous patency without the occurrence of a total occlusion (complete obstruction or a closure of a passageway or vessel determined by DUS or contrast angiogram) of the original lesion, and

Amendment #1: 15Jul13

Confidential

- without a re-intervention due to a clinically driven restenosis or occlusion to treat a partial or total occlusion of the stented segment,
- or bypass of the stented segment due to clinically-driven restenosis or occlusion

The primary patency will be calculated on a per lesion basis – for purpose of analysis in cases in which multiple lesions are covered by one stent then the stented segment will be considered as one lesion. The cumulative incidence of patency at 9 months will be computed as the number of lesions that met primary patency divided by the number of subject-lesions for the population being analyzed.

Change from Baseline in Systolic Blood Pressure

Systolic blood pressure will be assessed at each follow-up study visit. Blood pressure measurements will be obtained with a certified, calibrated, and validated equipment. Subjects will be instructed to refrain from exercise, smoking or caffeine ingestion for 30 minutes before blood pressure measurement, and measurements will be obtained after at least 5 minutes of rest. At each time point, a minimum of three (3) readings separated by 2 minutes will be averaged.

The primary clinical outcome is the improvement in systolic blood pressure (SBP) at 9-months as compared to baseline systolic blood pressure computed as follows:

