8.8 Unit of Analysis

For the primary functional endpoint of primary patency rate the unit of analysis is the atherosclerotic lesion(s). The rationale for analyzing the primary endpoint following a per lesion approach, is to avoid overestimation of the failure rate, as more lesions would be at risk for restenosis but would not be accounted for in a per subject analysis.

Since blood pressure is measured on the subject level, the primary clinical endpoint of change SBP will be evaluated at the subject level.

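### The 70% patency goal is built from restenosis rates, but no section says whether an untreated ≥60% restenosis, or an incidental TLR, is a patency failure

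*Protocol*

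**What the plan says.** **The goal.** Protocol 5.2.1 pools restenosis rates from bare-metal stent series (Table 3; assessed by DUS, angiography or CTa) to 21.4% and takes 40% for PTRA. It then chooses "a restenosis rate of 30% leading to a Performance Goal for primary patency set at 70" per cent. The stated property is: "This goal will preserve at least 50% of the difference between the currently available bare metal stent rate and the PTRA rate". A second purpose is to allow for more severe lesions than in earlier studies. SAP 5.6 repeats this derivation.

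**The endpoint.** Protocol 2.2, 5.1 and Appendix 2 require continuous patency with no total occlusion and "without a re-intervention to treat a partial or total occlusion of the stented segment, or bypass of the stented segment". A closing phrase about clinically driven restenosis or occlusion can be read as applying to bypass alone or to re-intervention as well. SAP 7.6.1 settles that phrase one way: "without a re-intervention due to a clinically driven restenosis or occlusion to treat a partial or total occlusion of the stented segment". Appendix 2 defines restenosis (≥60% narrowing or a recurrent gradient) as a separate term. Incidental TLR is a separate secondary endpoint.

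**The imaging.** At 9 months, a DUS showing ≥60% stenosis, or one that stays non-diagnostic, leads to an angiogram to grade restenosis (Protocol 3.0, SAP 5.1 and 7.6.1). No section links that grade to patent or failed.

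**The analysis.** SAP sections 2 and 6.2 call all inference descriptive after enrolment stopped at 68 subjects. SAP 9.9 still deems one-sided p below 0.025 significant, and 9.9.1 still sets patency against 70% with a p-value. SAP 9.11.8 plans subject-level counts of DUS below and at or above 60%. SAP 9.11.10 plans summaries of core-lab angiography.

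**The concern.** A performance goal carries its meaning only on the scale on which it was derived. Here that scale is restenosis found by imaging. If a lesion that has restenosed to ≥60% but has not been treated is counted as patent, the observed rate is measured on a more lenient scale than the goal. Meeting 70% would then not by itself show that half of the difference between bare-metal stents and PTRA is kept.

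If restenosis was meant to count, the problem is different but still practical: an analyst who programs the written definition will count those lesions as successes. Either way the numerator of the primary rate is not fully defined, and a descriptive rate needs a defined numerator as much as a tested one does.

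**Working it through.** **1. The plan's own figures.** Exact one-sided binomial, n = 125, null 0.70, true patency 0.82 (Protocol 5.2). The pass mark is the smallest x with P(X ≥ x | 0.70) ≤ 0.025. This gives x = 98, so 27 failures are allowed, with attained level 0.0230 and power 87.6%. The protocol's 27 failures and 87% reproduce. The margin preserved by a 30% limit is (40 − 30)/(40 − 21.4) = 0.538, so the claim of at least 50% is right on the restenosis scale.

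**2. Pass marks at the achieved size.** For 68 lesions the mark is 56 (level 0.0150). For 82 lesions (68 × 1.2, the lesions-per-patient figure in Protocol 2.1) it is 66 (level 0.0223).

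**3. Effect of the definition.** Take a stent at exactly 30% restenosis, which should pass at most 2.5% of the time. Let f be the share of restenoses that end as counted failures. Then the failure rate is 0.30 × f and the chance of passing is P(X ≥ pass mark | n, 1 − 0.30f). The documents do not give f, so it is an assumption shown over a range, with lesions treated as independent:

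| f | failure rate | n = 68 | n = 82 | n = 125 |
|---|---|---|---|---|
| 1.0 | 30% | 1.5% | 2.2% | 2.3% |
| 0.90 | 27% | 5% | 8% | 10% |
| 0.75 | 22.5% | 21% | 31% | 45% |
| 0.60 | 18% | 55% | 70% | 88% |
| 0.42 | 12.6% | 92% | 97% | 99.8% |

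**4. Where 0.42 comes from.** Ten series appear in both Table 3 and Table 4. Their TLR is 76/889 = 8.55%. Their Table 3 restenosis is 20.1% weighted by subjects and 20.2% by arteries. The ratio is about 0.42 (0.40 to 0.47 leaving out one series at a time). Single series run from 0 (0/42 against 14%) to about 1 (8/27 against 30%). This is only a rough guide: it sets per-subject TLR against mostly per-artery restenosis, at unmatched times, and leaves out untreated occlusions, which do count as failures here.

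**5. What the text suggests was meant.**
- *For counting restenosis:* the planning value of 82% patency implies 18% failures, close to the 21.4% restenosis rate. At f = 0.42 it would imply 18/0.42 ≈ 43% restenosis, worse than the 40% taken for PTRA. Protocol 2.1 says a detected stenosis is to be validated so that patency can be assessed definitively. SAP 7.6.1 places the imaging algorithm under the patency endpoint. Protocol 2.1 argues that a per-patient analysis would "overestimate the failure rate compared to a per lesion analysis, as more lesions would be at risk for restenosis", and SAP 8.8 chooses the lesion as unit to "avoid overestimation of the failure rate, as more lesions would be at risk for restenosis". Some articles were dropped in Protocol 5.2.1 because "definitions used for restenosis were outside of our trial design".
- *Against:* Protocol 2.1 and SAP 5.2 prefer the physician's clinical care to DUS restenosis alone as the measure of stent performance.

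None of these is a rule.

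**The case against.** The strongest reply has four parts.

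- **The endpoint may be a reasoned choice.** The documents explain why treatment decisions were preferred to DUS restenosis. That stands as a reason for the endpoint. It does not explain why a goal derived from restenosis rates fits it.
- **The size is not known.** The chance of passing runs from 1.5% to 92% at n = 68. A reader might infer from the ratio of 0.42 that an inadequate stent would very probably pass. The documents do not support that: the ratio has the weaknesses listed above, and a protocol-driven angiogram or counting incidental TLRs could raise the share. What stands is the direction and the range.
- **Restenosis is already summarised.** This is correct: subject-level DUS counts and summaries of core-lab angiography are planned. What is missing is narrower, namely a per-lesion composite set against 70%. SAP 6.2 limits sensitivity analysis to the per-protocol population.
- **The trial is now descriptive.** There is no Type I error control (SAP 8.7), and no planned analysis concludes that the margin was preserved. This lowers the stakes but does not remove them, because the comparison with 70%, its p-value and the significance threshold remain.

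**Conclusion.** The concern holds as a gap in definition with a known direction. On the literal text, untreated ≥60% restenoses count as patent, and the comparison with a restenosis-based 70% favours the device. For a stent at 30% restenosis and 68 lesions, the chance of passing is 1.5% at a share of 1.0, 21% at 0.75 and 92% at 0.42. These figures rest on an assumed share and on independent lesions.

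A reader might go further and infer that goal and endpoint are irreconcilable, or that the goal is invalid. The documents do not support this. Several passages, above all the 82% planning value, suggest that restenosis was meant to count, and the CEC Charter, which is not among these documents, may hold the rule. Nor do the documents settle that it was meant to count. The point should be fixed, in proportion to a descriptive analysis. Confidence is medium.

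**What to change.** 1. In SAP 7.6.1 and 9.9.1, state whether (a) an untreated core-lab ≥60% restenosis and (b) an incidental TLR are patency failures. If the CEC Charter has the rule, quote it. Reconcile the wording with Protocol 2.2.
2. Keep the prespecified analysis. Beside it, report a per-lesion restenosis-inclusive patency rate with its exact confidence interval against 70%. Failure is total occlusion, any target-lesion re-intervention, bypass, or core-lab angiography-confirmed ≥60% restenosis by the 9-month window, treated or not. Give the number of lesions without a diagnostic image.
3. List this in SAP 6.2 as added after enrolment stopped.
4. State that the 50%-preservation reasoning was built on restenosis rates, so meeting 70% on the written definition does not by itself show it. The restenosis-inclusive rate is the closer match but not an exact one: Table 3 mixes imaging methods and follow-up times and shows no restenosis thresholds.

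The cost is a few lines of SAP text, one derived variable and one table row, from imaging already collected. The added rate will be the same or lower, some lesions may be unclassifiable, and the variable is late and open-label, so it must be labelled as such.

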### Clinical Endpoint

Improvement in systolic blood pressure (SBP) at 9-months as compared to baseline systolic blood pressure.

## **2.3 SECONDARY ENDPOINTS**

The secondary endpoints will provide:

1. The occurrence of procedure-related MAEs reported as percentage of subjects with MAE, at 30-days, 9-months, 12-months, 24-months, and 36-months.  
Inclusive of:
  - a. Procedure-or device-related occurrence of death
  - b. Q-Wave MI
  - c. Clinically driven TLR
  - d. Significant embolic events
    - i. Defined as unanticipated kidney/bowel infarct clinically driven by symptoms of abdominal or back pain and confirmed with CT scan or open surgery, lower extremity ulceration or gangrene, or kidney failure after 30-days, 9-months, 12-months, 24-months, and 36-months.
2. Technical success defined as successful delivery and deployment of the iCAST™ RX Stent System with  $\leq 30\%$  residual angiographic stenosis after covered stent deployment (including post-dilatation) assessed via QVA by an independent core laboratory.
3. Procedural success defined as technical success without the occurrence of MAE prior to hospital discharge.
4. TLR measured as the proportion of subjects that require a clinically-driven reintervention of the target lesion through 9-months.
  - a. A clinically-driven TLR is defined as a TLR (PTA, bare metal stent or repeat covered stent deployment, or surgical bypass) due to documented recurrent hypertension from 30-days post-procedure level and/or deterioration in renal function from baseline value, associated with angiographic core laboratory adjudication of a  $\geq 60\%$  diameter covered stent restenosis.
5. Rate of incidental TLR defined as rate of TLRs not meeting the definition of a

clinically driven TLR.

6. Improved SBP control assessed at 30-days, 9-months, 12-months, 24-months and 36-months.
7. Secondary patency rate at 9-months after a clinically-driven TLR which restores patency after total occlusion.
8. Change in number and dosage of anti-hypertensive medications as compared to baseline.
9. Renal function compared to baseline as measured by eGFR at 30-days and 9-months.

### **3.0 TRIAL DESIGN AND POPULATION**

This is a prospective, single-arm, multicenter clinical trial that will take place at up to 25 US/OUS sites. Primary endpoints have been determined to show the safety, effectiveness, and clinical outcomes of the iCAST™ RX Stent System. Safety and effectiveness will be evaluated based on the primary patency rate at 9-months on a per lesion basis evaluated against a performance goal of published studies with bare-metal stents. The primary clinical endpoint will assess the improvement in systolic blood pressure at 9-months as compared to baseline systolic blood pressure.

Eligible subjects will undergo a two-week Medical Documentation Screening period to confirm resistant hypertension (SBP  $\geq$  155mmHg) while on maximum tolerable dose of  $\geq$  three anti-hypertensive medications from at least three classes of drugs, one of which must be a diuretic.

There must be documented clinical evidence to support likelihood of angiographic findings  $>$  80% whether it is DUS, CTa, MRa or other medical evidence. After meeting screening and clinical eligibility criteria, subjects will undergo a baseline assessment for angiographic eligibility. After angiographic documentation of a  $\geq$  80% diameter renal artery stenosis or FFR  $<$  0.8 is confirmed the subject may be enrolled in the trial by placement of the investigational device.

The 9-month visit will include a follow-up DUS of the target renal artery. If the DUS is non-diagnostic due to an imaging problem, such as overlying bowel gas or body habitus, a second DUS may be attempted. If the DUS is indicative of  $\geq$  60% stenosis as determined by the core laboratory, or the second DUS remains non-diagnostic, a contrast angiogram will be used to assess the degree of restenosis of the covered stent(s).

Clinical follow-up visits will be required for all enrolled subjects at 30-days, 9-months, 12-months, 24-months and 36-months. A 6-month and 18-month visit will occur via telephone to

collect medication usage and AEs only. The 36-month clinic office visit will be required as the final safety visit.

### **3.1 DETERMINATION OF TRIAL ELIGIBILITY**

Subjects eligible for initial trial screening will present with renal artery stenosis and meet ALL of the inclusion criteria in order to be considered for the ARTISAN trial. If ANY of the exclusion criteria are met, the subject cannot be enrolled in the trial or treated using the investigational device.

The Medical Monitor will provide oversight in the enrollment of subjects during the course of the trial. All potential subjects will be reviewed and approved by the Medical Monitor, prior to enrollment, to ensure the subjects have met all general Inclusion/Exclusion criteria. Once the subject has been reviewed and approved by the Medical Monitor, the subject may proceed to the index procedure.

A subject is deemed enrolled into the trial once all inclusion criteria have been met and reviewed by an independent medical monitor, no exclusion criteria exist, the operator determines the target lesion is  $\geq 80\%$  diameter stenosis or FFR  $< 0.8$  and the trial device enters the subject. All adult subjects will be counseled on and instructed to read and sign the required ICF prior to conducting any trial related procedures.

### **3.2 INCLUSION CRITERIA**

Subjects must meet ALL of the inclusion criteria to be considered for the trial:

General Inclusion Criteria:

1. Age  $\geq 18$  at the time of informed consent.
2. Subject or subject's legal representative have been informed of the nature of the trial, agrees to participate and can comply with study procedures and follow-up, and has signed an IRB/EC approved ICF.
3. Subjects that have bilateral kidneys or a solitary functioning kidney with Renal Artery Stenosis in at least one kidney and an average SBP  $\geq 155\text{mmHg}$ .
4. Subject has a history of maximum tolerable dose of  $\geq 3$  anti-hypertensive medications of different classes, one of which must be a diuretic (for at least two weeks prior to Medical Documentation Screening period).
  - a. A documented history for a minimum of 3 months showing reasonable and aggressive efforts to manage hypertension prior to consent. This must include the use of a broad variety of medications that have been used and failed or not tolerated.
5. Subject must have documented clinical evidence to support likelihood of angiographic findings  $> 80\%$  whether it is DUS, CTa, MRa or other medical evidence..
6. NYHA class I, II, or III the time of trial enrollment.

NOTE: When a subject has bilateral Renal Artery Stenosis both of which require stenting, it is recommended to treat both kidneys with an iCAST™ RX Stent System during the index procedure. In the event that a subject needs a renal stenting procedure staged for renal protection, it is important that the Investigator treats the second renal artery with an iCAST™ RX Stent System after 30 days of the index procedure. If subjects with bilateral stenosis have only one lesion that meets protocol inclusion criteria that lesion should be treated per protocol. The recommendation is to NOT treat the second non-qualifying lesion, however if the operator feels strongly it is indicated, then they should treat per standard of care after 30-days post index procedure in order to comply with exclusion criteria #10.

Subjects with flash pulmonary edema are allowed into the trial should they meet all other Inclusion and Exclusion criteria.

Angiographic Anatomic Inclusion Criteria:

1. Angiographic diameter renal artery stenosis  $\geq 80\%$  involving unilateral or bilateral renal arteries.
  - a. The degree of percent diameter stenosis for all lesions intended to be treated, must be confirmed via one of the following methods:
    - i. Manual or automated measurement with calipers
    - ii. Measured FFR  $< 0.8$  using a pressure wire
    - iii. Measured translesional peak pressure gradient of  $> 21\text{mmHg}$  after induced hyperemia via dopamine or papaverine using a 4Fr or less catheter or pressure wire.
  - b. Subjects with 60-79% angiographic stenosis who have confirmed FFR  $< 0.8$  may be enrolled.
2. Renal pole-to-pole length  $\geq 8\text{cm}$  (per visual estimate).
3. Target lesion length  $\leq 16\text{mm}$  per vessel (per visual estimate).
4. Renal artery vessel diameter  $\geq 5.0\text{mm}$  and  $\leq 7.0\text{mm}$  (per visual estimate).
5. Lesion originating  $\leq 15\text{mm}$  of the renal ostium.

